Control participants will be enrolled from the communities surrounding participating health care facilities for two reasons. First, interpreting the results of some diagnostic tests requires knowledge of background prevalence of infection or colonization in the study population. Community controls will provide samples to estimate this background for each study site. Second, a healthcare utilisation survey (focusing on fever episodes and treatment seeking) administered to control participants will allow us to estimate the incidence and burden of specific causes of fever in the study settings.

This study provides a unique opportunity to collect and store biomedical samples with data from a large and well-characterised group of febrile patients and controls from representative settings in sub-Saharan Africa and Southeast Asia. The samples will be useful for identification of novel diagnostic targets, and for development and evaluation of new point-of-care diagnostic tests intended to guide the management of febrile patients. New tests could include those that predict severity of illness, detect specific infections, and/or differentiate between bacterial and viral infections, as identified as a high priority at a WHO meeting of experts convened in 2015.¹⁸ Informed consent will be sought for study participation, and for storage and future use of data and biological samples.

For clinicians to be able to appropriately use new knowledge on aetiologies of fever, diagnostic tests, and antimicrobial resistance data to manage febrile patients, research evidence must be integrated into clear guidelines. Implementation of clinical algorithms,

such as IMCI or integrated Community Case Management (iCCM), has shown that health care workers are able to adopt and apply recommendations when reasonable support is provided.²⁰ The design and support for these guidelines must take into account end users' perceptions and patients' preferences in order to ensure good adherence and optimise impact. These issues will be addressed in qualitative work conducted alongside and linked to the FIEBRE study, which will be presented in a separate social science research protocol.

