7.5 Community controls

Interpreting the results of some serological assays and pharyngeal swab assays requires knowledge of background prevalence of infection or colonization in the study population. To address this, 600 community controls (section 11.3 sample size calculations), frequency matched by age, sex, month of enrolment (to address seasonality), and geographical area to the cases, will be selected from the community living in the catchment area of the health facility for each site. No controls will be specifically recruited for the inpatient population, who may come from a wider geographic area. However, an analysis comparing controls with our sample of in-patients who do come from the area from which controls were selected, will be carried out.

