1) To generate data on incidence of specific infections among study participants, and therefore contribute key data on disease burden for some infections that are not counted in current “global burden of disease” estimates;

For an area whose population size is known, a health utilization survey will be used to estimate r , the proportion of fevers for which treatment was sought at a study centre. The total number of cases seen at the study site from the defined population will be multiplied by $1/r$, to obtain the total cases in a year from the defined population. This will be divided by the size of the population to estimate incidence. Incidence of fever caused by specific pathogens will be calculated by multiplying the incidence by the AF for that pathogen.

3) Evaluation of available biomarker assays to assess their performance and potential utility in fever case management in the study areas;

The sensitivity, specificity, and positive and negative predictive value of each biomarker will be estimated.

4) To generate data to support the development of new fever case management algorithms which may be evaluated in future studies;

The association between the presence of pathogens with predefined clinical and other variables will be examined.

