11.2 Sample size considerations

Any single pathogen or aetiology is assumed to be likely to be rare in the study populations.^{2,14,15} To identify causes of fever, a sample size of 600 patients per group will enable estimation of the prevalence of an infection whose true prevalence is 5% with a precision of +/- 1.7% with 95% confidence, and to estimate the prevalence of an infection whose true prevalence is 1% with a precision of +/- 0.8% (see Table 3).

Table 3. Sample size estimates for varied infection prevalences

Number of participants	Prevalence	Confidence interval
600	5%	+/- 1.7
600	2%	+/- 1.1
600	1%	+/- 0.7

Since blood cultures and convalescent samples will not be taken from community controls, the prevalence of respiratory viruses (e.g., influenza and RSV) detected by polymerase chain reaction (PCR), and of baseline seropositivity to other pathogens, will be compared in cases and controls. The prevalence of respiratory viruses, and of seropositivity to common causes of fever, is assumed to be approximately 5% in the general population. A sample of 600 outpatients and 300 controls will provide >90% power to show a significant difference between a prevalence of 12% in cases and 5% in controls. Therefore, 600 febrile patients will be enrolled in each of four analysis groups (children aged ≥ 2 months to <15 years as inpatients and outpatients, and inpatients and outpatients aged ≥ 15 years), for a total of 2400 patients per site; plus 300 controls in each of the two age groups at each site (total 600).

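### Secondary objective 4 relates clinical variables to pathogen presence; where background carriage or seropositivity exists, this attenuates odds ratio and sensitivity and overstates the probability that the pathogen caused the fever

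*Protocol*

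**What the plan says.** Protocol section 11.1 restates secondary objective 4 as "To generate data to support the development of new fever case management algorithms which may be evaluated in future studies" and gives one sentence of analysis: "The association between the presence of pathogens with predefined clinical and other variables will be examined". It mentions no AF, case definition or control comparison there.

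Elsewhere the protocol separates detection from cause:

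- Section 3.2, on why controls are enrolled: "interpreting the results of some diagnostic tests requires knowledge of background prevalence of infection or colonization in the study population".
- Section 7.5: "Interpreting the results of some serological assays and pharyngeal swab assays requires knowledge of background prevalence of infection or colonization in the study population".
- Section 11.2, on the background level: "The prevalence of respiratory viruses, and of seropositivity to common causes of fever, is assumed to be approximately 5% in the general population".
- Section 11.1 uses case-control odds ratios and AFs for primary objective 1, sub-group AFs for primary objective 2, and incidence multiplied by the AF for secondary objective 1.

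Section 7.6 places the case definitions for causes of fever in Appendix E, which is not at hand. Under section 7.5.3 controls give no blood culture, urine or convalescent serum. Under section 7.5 no controls are recruited for inpatients as such; only inpatients from the control area can be compared.

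**The concern.** An algorithm needs the probability that a fever is due to a pathogen, given what the clinician sees. A patient who merely carries a respiratory virus, or has an old antibody response, shows the signs of whatever else caused the fever. Counting that patient as a case of the pathogen moves the sign's frequency among positives toward its frequency in everyone else. The odds ratio and sensitivity fall. The proportion positive exceeds the proportion caused, in patients with and without the sign alike. The protocol sets up controls to handle this and uses them for three other objectives, but the outcome it names for objective 4 leaves them out.

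**Working it through.** **Inputs from the protocol (section 11.2).** Prevalence 12% in 600 outpatients and 5% in 300 controls.

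**Assumptions.** Two-sided alpha of 0.05. Patients whose fever has another cause carry the pathogen at the control prevalence. Incidental positives show a sign as often as other patients do. The sign occurs in 60% of fevers due to the pathogen and in 20% of others; a range follows.

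**1. The plan's own figure.** The protocol says its sample "will provide >90% power to show a significant difference between a prevalence of 12% in cases and 5% in controls". Pooled prevalence = (72 + 15)/900 = 0.0967. Null SE = √(0.0967 × 0.9033 × (1/600 + 1/300)) = 0.0209. Alternative SE = √(0.12 × 0.88/600 + 0.05 × 0.95/300) = 0.0183. Power = Φ((0.07 − 1.96 × 0.0209)/0.0183) = 94.4%. The statement reproduces.

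**2. Incidental share.**

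- OR = (0.12/0.88)/(0.05/0.95) = 2.59.
- AF = p(1 − 1/OR) = 0.12 × (1 − 0.386) = 0.0737.
- Of 72 positives in 600, 44.2 are caused and 27.8 incidental: 1/OR = 39% (5/12 = 42% by simple division).
- With 5% in controls, the incidental share would be 61% if 8% of cases were positive and 21% if 20% were.

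**3. The sign analysed by presence.**

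| Patients | Number | With sign |
|---|---|---|
| Positive, caused | 44.2 | 26.5 |
| Positive, incidental | 27.8 | 5.6 |
| Negative | 528 | 105.6 |

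- Sensitivity = (26.5 + 5.6)/72 = 44.6%, against 60%.
- OR = (32.1 × 422.4)/(39.9 × 105.6) = 3.2, against (0.6/0.4)/(0.2/0.8) = 6.0.
- With the sign (137.7 patients): positive 32.1/137.7 = 23.3%; caused 26.5/137.7 = 19.3%.
- Without it (462.3 patients): positive 39.9/462.3 = 8.6%; caused 17.7/462.3 = 3.8%.

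**4. Range over signs, same 12% v 5%.** A 50%/30% sign gives OR 1.7 instead of 2.3. An 80%/20% sign gives 5.3 instead of 16.

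**5. AF by sign.** For a patient group with positivity q, p(1 − 1/OR) equals q − (1 − q) × 0.05/0.95.

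- With the sign: 0.2330 − 0.7670 × 0.0526 = 19.3%.
- Without it: 0.0863 − 0.9137 × 0.0526 = 3.8%.

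Both match the true values in step 3.

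**6. Power.** The AF is linear in q, so the AF difference is the presence difference divided by 0.95: 14.7 points becomes 15.4. The z for the difference is about 3.8 either way in one group of 600 outpatients.

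**7. The printed AF formula.** Section 11.1 prints p(1 − OR), which gives 0.12 × (1 − 2.59) = −0.19 on these figures and is negative whenever OR exceeds 1.

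**The case against.** The sentence is short, the objective only generates data for later work, and a statistical analysis plan may define the outcome more closely. Case definitions exist, and patients have paired serology, so a positive result may already mean more than raw detection. Sub-group AFs are planned for primary objective 2. The size shown rests on assumed sign frequencies and on a power scenario.

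Much of this limits the scope. Blood-culture and paired-serology diagnoses are little affected. Controls cannot correct results they were never tested for, cover inpatients only from the control area, and allow a group-level correction without labelling any individual as a carrier. Section 11.1 allows inpatient AFs to be dropped if too few come from that area.

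It does not remove the point. The protocol does more than leave a detail open: it names presence as the outcome, cites no case definition there, and does not list clinical signs among the planned AF sub-groups.

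A reader might go further than the documents allow in three ways:

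- *Useful signs would be discarded.* No rule for dropping signs is stated. The 60%/20% sign would be found by presence with about 99% power on the log odds ratio scale, and the AF adds none.
- *Predictive value is diluted.* The probability of disease is inflated (23.3% v 19.3%; 8.6% v 3.8%). It is the odds ratio and sensitivity that shrink.
- *The protocol says malaria results need background data.* Sections 3.2 and 7.5 do not name malaria. It belongs here only where controls, who are also tested under section 7.6, prove parasitaemic.

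**Conclusion.** The point holds for swab NAAT, single-sample serology and, where controls show parasitaemia, malaria. It applies to outpatients and to inpatients from the control area. Following the text as written would roughly halve the assumed sign's odds ratio (6.0 to 3.2), cut its sensitivity from 60% to 45%, and overstate the probability of caused fever by 4.0 points with the sign and 4.8 without. The relative error is much larger without the sign, where 8.6% is more than twice 3.8%.

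Only the 12% and 5% are the protocol's; the sign frequencies are assumed. The direction does not depend on them, provided that incidental positives resemble other patients. The size grows with the incidental share. Detection of signs is not at risk, and neither culture nor paired-serology diagnoses are materially affected.

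**What to change.** Amend the objective 4 text in section 11.1:

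- For pathogens with background carriage or seropositivity, in outpatients and in inpatients from the control area, report alongside presence the AF in patients with and without each prespecified sign. Use the same controls and adjustment as for primary objective 1, and compare the AFs as a difference with bootstrap intervals.
- Correct the AF formula to p(1 − 1/OR) first.
- For blood-culture, urine-culture and paired-serology diagnoses, use the case-definition aetiology in Appendix E.

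No new data are needed. The gain is in the two AF levels; the difference itself hardly moves.

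The cost is precision, because each AF also carries control sampling error. For patients without the sign, the variance of the positivity is 0.0863 × 0.9137/462.3 = 0.000171, a 95% half-width of 2.6 points. By the delta method the AF variance is 0.000171/0.95² + 0.9137² × (0.05 × 0.95/300)/0.95⁴ = 0.000351, a half-width of 3.7 points around 3.8%. With the lower limit so near zero, AF ratios are unstable in a single site-age group. Use differences, or pool sites where needed.

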11.2 Sample size considerations

Any single pathogen or aetiology is assumed to be likely to be rare in the study populations.^{2,14,15} To identify causes of fever, a sample size of 600 patients per group will enable estimation of the prevalence of an infection whose true prevalence is 5% with a precision of +/- 1.7% with 95% confidence, and to estimate the prevalence of an infection whose true prevalence is 1% with a precision of +/- 0.8% (see Table 3).

Table 3. Sample size estimates for varied infection prevalences

Number of participants	Prevalence	Confidence interval
600	5%	+/- 1.7
600	2%	+/- 1.1
600	1%	+/- 0.7

Since blood cultures and convalescent samples will not be taken from community controls, the prevalence of respiratory viruses (e.g., influenza and RSV) detected by polymerase chain reaction (PCR), and of baseline seropositivity to other pathogens, will be compared in cases and controls. The prevalence of respiratory viruses, and of seropositivity to common causes of fever, is assumed to be approximately 5% in the general population. A sample of 600 outpatients and 300 controls will provide >90% power to show a significant difference between a prevalence of 12% in cases and 5% in controls. Therefore, 600 febrile patients will be enrolled in each of four analysis groups (children aged ≥ 2 months to <15 years as inpatients and outpatients, and inpatients and outpatients aged ≥ 15 years), for a total of 2400 patients per site; plus 300 controls in each of the two age groups at each site (total 600).

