11.1 Quantitative outcome measures and analysis

Listed by study objective:

- 1) To determine the treatable and/or preventable causes of fever in children and adults presenting as outpatients, and among those admitted to hospitals, in areas represented by the study sites;

For outpatients the attributable fraction (AF) will be calculated for each pathogen or group of pathogens. This will be done separately for each site and age stratum. For each group of patients, the odds ratio (OR) for the association between each pathogen and fever will be calculated by comparing cases and controls. Logistic regression will be used to calculate the odds ratio. In order to take the matched design into account, strata based on geographical location and season will be defined at each site and the analysis will be adjusted for age, sex and stratum. Since cases and controls are recruited at a constant rate throughout the year but fever incidence is likely to vary by season, the analysis will be weighted by the proportion of patients included in the study of the total number of cases seen at the study

site in the given season. AF will then be calculated as $AF_A = p_A(1-OR_A)$. Confidence intervals will be calculated in an appropriate way, e.g. bootstrapping or delta method.

For inpatients, first the distribution of diagnoses in each site will be tabulated for all inpatients in the study. Then a second analysis to calculate AFs will be carried out for inpatients, but this will be restricted to inpatients who come from the same geographical area as the controls. The calculation of AFs for inpatients may be dropped if insufficient numbers of in-patients come from the same area as the controls.

- 2) To determine how fever aetiology varies according to patient age, level of the health system, geographical area, local malaria and HIV prevalence, and other risk factors;

Stratified analyses will be carried out as above to estimate the AF for sub-groups of patients.

- 3) To determine the prevalence and spectrum of antimicrobial resistance among bacterial pathogens identified in clinical specimens from febrile patients;

At each site the proportion of bacterial pathogens with antimicrobial resistance defined by standardized criteria will be calculated. The proportion of common organisms demonstrating resistance to a standard panel of antibiotics will be reported.

Specific secondary objectives:

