16 ANTICIPATED POTENTIAL PROBLEMS

Table 5. Potential study problems and proposed solutions

Potential problem	Proposed solution
Delayed start of study activities due to delays in ethics approvals, procurement, other logistic impediments	
 1) Work with relevant personnel/agencies, local and national authorities as needed to minimize impact on project timelines 2) If necessary discuss with DFID re: adjustment of deliverables timeline
Insufficient sample size (for cases and/or controls), or slower than expected enrolment	
 1) Work with local community leaders, health facility staff and other relevant personnel to identify and address possible causes 2) Increase number of clinical sites (within the same geographical/population area)
High (>15%) loss to follow-up	
 1) Reinforce importance of full follow-up in informed consent discussion and at study visits 2) Increase home visit staff
Adverse events and/or protocol violations	
 1) Report to appropriate ethical committee and EOC 2) Prevention as appropriate through protocol amendment and/or personnel training
Loss of or damage to blood samples and isolates during storage or transport	
 1) Minimize risk with use of good-quality equipment, SOPs and training at sites, and use of well-established international courier 2) Reserve a portion of each sample at study site in addition to LSHTM archive

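### Table 3 misstates one precision figure (0.7 for 0.8), and its figures, which are for a raw prevalence, do not carry over to the outpatient attributable fraction

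*Protocol*

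**What the plan says.** Section 11.2 of the protocol introduces its precision figures as serving to identify causes of fever. It says that "a sample size of 600 patients per group will enable estimation of the prevalence of an infection whose true prevalence is 5"%, and puts the 95% half-width in that case at 1.7 points. It adds that the same number suffices "to estimate the prevalence of an infection whose true prevalence is 1% with a precision of +/- 0.8"%. It refers to Table 3, which lists +/- 1.7, 1.1 and 0.7 for prevalences of 5%, 2% and 1% with 600 participants.

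For the comparison with controls, the section says that the prevalence of respiratory viruses and of seropositivity "is assumed to be approximately 5% in the general population". It claims more than 90% power for 12% in 600 outpatients against 5% in 300 controls. The controls are set at "plus 300 controls in each of the two age groups at each site (total 600").

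Section 11.1 defines the measures. "For outpatients the attributable fraction (AF) will be calculated for each pathogen or group of pathogens", separately by site and age stratum, from a case-control odds ratio. Inpatients are handled differently: "For inpatients, first the distribution of diagnoses in each site will be tabulated for all inpatients in the study". Inpatient AFs come second, only for patients from the controls' area, and may be dropped.

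**The concern.** There are two separate matters. First, the text and the table of one section give different precision for identical inputs, so one of them is wrong.

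Second, the precision offered for identifying causes of fever is that of a single proportion. For outpatients the protocol measures causes by the AF, which depends on the prevalence in cases and in controls. Section 11.1 then multiplies fever incidence by that AF to obtain pathogen-specific incidence. A reader who takes 1.7, 1.1 or 0.8 points as the precision of an outpatient cause of that size will expect narrower intervals than the case-control comparison can give, most of all for the rare causes that section 11.2 says are likely.

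**Working it through.** **Inputs from the protocol.** 600 patients per group, 95% confidence, prevalences of 5%, 2% and 1%, 300 controls per age group, background about 5%, and the 12% v 5% scenario (all section 11.2).

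**Step 1. Reproduce Table 3.** Half-width = 1.96 × sqrt(p(1−p)/600), in percentage points.

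| Prevalence | Computed | Text | Table 3 |
|---|---|---|---|
| 5% | 1.744 | 1.7 | 1.7 |
| 2% | 1.120 | not given | 1.1 |
| 1% | 0.796 | 0.8 | 0.7 |

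Only the 0.7 fails. Other interval methods do not rescue it: at 1%, Wilson gives 0.853, Clopper-Pearson 0.898, and a multiplier of 2 gives 0.812. A 90% interval gives 0.668, but would make the other rows 1.46 and 0.94. A true +/- 0.7 needs 1.96² × 0.0099/0.007² = 776.1, so 777 patients. Truncating instead of rounding would give 1.7, 1.1 and 0.7, which is a plausible source of the slip.

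**Step 2. Reproduce the power statement.** Pooled prevalence = (72 + 15)/900 = 0.0967. Null standard error = sqrt(0.0967 × 0.9033 × (1/600 + 1/300)) = 0.02090. Alternative standard error = sqrt(0.12 × 0.88/600 + 0.05 × 0.95/300) = 0.01828. Then (0.07 − 1.96 × 0.02090)/0.01828 = 1.59, which gives power of 94.4%. The claim of more than 90% holds.

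**Step 3. Precision of the AF.** With p the prevalence in cases and q in controls, AF = p(1 − 1/OR) = (p − q)/(1 − q). Section 11.1 prints p(1 − OR), which is negative for any OR above 1 (−19.1% for 12% v 5%). That is a separate matter, and the form with 1/OR is used here. The delta method gives

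Var(AF) = p(1−p)/[600(1−q)²] + [(1−p)/(1−q)²]² × q(1−q)/300.

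For 12% v 5%: AF = 0.07/0.95 = 7.4%. Variance = 0.000195 + 0.000151 = 0.000346, so the half-width is 1.96 × 0.01859 = 3.6 points. The raw 12% prevalence in the same 600 patients has 2.6.

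For a given AF at 5% background, p = 0.05 + 0.95 × AF:

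| AF | p in cases | AF half-width | 95% interval | Raw half-width at a prevalence of that size |
|---|---|---|---|---|
| 5% | 9.75% | 3.51 | 1.5 to 8.5 | 1.74 |
| 2% | 6.90% | 3.32 | −1.3 to 5.3 | 1.12 |
| 1% | 5.95% | 3.25 | −2.3 to 4.3 | 0.80 |

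**Step 4. Dependence on background.** Backgrounds of 1% and 2% are assumptions, shown for range. For AFs of 5%, 2% and 1% the half-widths are 2.58, 2.25 and 2.12 points at 2% background, and 2.20, 1.77 and 1.59 at 1%. At zero background they return to 1.74, 1.12 and 0.80.

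**Step 5. Paired serology.** Tests that need the day 28 sample have fewer than 600 results if any patient is lost. The protocol gives no expected rate, so these losses are assumptions:

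| Loss | n | 5% | 2% | 1% |
|---|---|---|---|---|
| 10% | 540 | 1.838 | 1.181 | 0.839 |
| 15% | 510 | 1.892 | 1.215 | 0.864 |
| 20% | 480 | 1.950 | 1.252 | 0.890 |

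**The case against.** The table slip is 0.1 point in one cell, and no sample size choice turns on it. Section 11.2 claims precision for the prevalence of an infection, and for that quantity the design delivers it. Raw prevalence is the right quantity for the inpatient tabulation. It also serves pathogens with almost no background: section 7.5.3 expects blood culture yield in controls to be close to zero, and step 4 shows that the AF then has the raw precision. The case-control comparison has its own power statement, which reproduces. Section 7.5.1 lets sites recruit more controls where capacity allows. AF precision could also be set out in an analysis plan that is not shown.

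Most of this stands and limits the point. A reader might infer that the design fails to deliver its stated precision. It does not fail for raw day 0 prevalence or for inpatient diagnoses made on day 0 samples. A reader might also take "High (>15%) loss to follow-up" in Table 5 (section 16) as a planned rate and so treat 510 patients as the design figure. The entry is a trigger for action in a list of potential problems, and the effect at 15% is modest (1.74 to 1.89 at 5%).

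Three things remain. The cell contradicts the text. The power statement covers one large contrast and says nothing about interval width for smaller AFs. Extra controls depend on site capacity: with one per outpatient (600 per age group), halving the second variance term gives 2.8 and 2.7 points for AFs of 2% and 1%, which still include zero at 5% background. An analysis plan could add AF precision, but the protocol itself offers a precision for identifying causes without saying that it does not apply to its outpatient measure.

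**Conclusion.** Table 3's 1% entry is wrong: 0.7 should be 0.8 (0.796), as the text has it. The remaining figures are correct for a raw prevalence in 600 patients with a result, and should not be read as the precision of the outpatient AF. At the protocol's 5% background the AF half-width is about 3.3 to 3.6 points over the cases examined, so an AF of 1% to 2% could not be told from zero, while an AF of 5% could.

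The AF figures rest on 600 cases, 300 controls, the 5% background, the form p(1 − 1/OR) and the delta method, without covariate adjustment or seasonal weights. Unequal weights would normally widen the intervals, but the protocol gives no weights and so no factor is applied. The documents do not support a statement about how many actual causes will have intervals that include zero, because that depends on pathogen-specific backgrounds that they do not give. Nor do they show that the sample size is inadequate for its stated purposes.

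**What to change.** In section 11.2:

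- Correct the 1% row of Table 3 to +/- 0.8.
- Label the Table 3 figures as the precision of a raw prevalence in 600 patients with a result.
- Beside the power statement, give AF half-widths for 600 cases and 300 controls at 5% background: about 3.6 points for 12% v 5%, and 3.5, 3.3 and 3.3 points for AFs of 5%, 2% and 1%. Say that they are unadjusted and unweighted, and name the AF formula used.
- Optionally, add rows for paired serology under a stated, assumed loss, from step 5.

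This is a change to one table and a few sentences. It needs no extra patients or controls. The only cost is that the stated precision looks less favourable.
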